Over all the doses studied, K0706 was well-tolerated with treatment related AEs largely limited to Grade 1-2. A total of [REDACTED] AEs were reported in [REDACTED] subjects. Out of [REDACTED] TEAEs, [REDACTED] TEAEs ([REDACTED]) were related to K0706 while [REDACTED] TEAEs ([REDACTED]) were unrelated to K0706. The most common AEs that occurred in [REDACTED] of the subjects included predominantly disorders of the [REDACTED] and [REDACTED] and [REDACTED] disorders (limited to grade 1 and 2). Treatment related [REDACTED] AEs included [REDACTED] of any grade experienced by [REDACTED] subjects ([REDACTED]), [REDACTED] any grade experienced by [REDACTED] subjects ([REDACTED]). A total of [REDACTED] treatment related SAEs have been reported and include: [REDACTED] in a subject dosed at [REDACTED] and moderate [REDACTED] in a subject dosed at [REDACTED].

Early signs of anti-leukemic activity have been observed in the subjects treated with K0706 as listed in Table 5-8.

[REDACTED]

[REDACTED]

The available preclinical and early efficacy and safety observed in Part B form the rationale to initiate Part C (Pivotal study) for K0706 in the subjects with Ph+ CML refractory or intolerant to ≥ 3 TKIs prior TKIs.

6 PART B

This study will be performed in compliance with the protocol, ICH GCP and applicable regulatory requirements. Aspects of the study concerned with the IMP will meet the requirements of the appropriate regulations.

6.1 RATIONALE

Rationale for Starting Dose and Schedule

The [REDACTED] showed a [REDACTED]
[REDACTED] A [REDACTED] was conducted in [REDACTED]
[REDACTED] mortality or severe clinical signs were observed up to a dose of [REDACTED]
[REDACTED]

Based on these findings, the human equivalent dose was calculated from the [REDACTED]
[REDACTED] of K0706. Upon application of the appropriate conversion factors and safety factors as recommended in the US FDA Guidance for Industry (2005), Estimating the Maximum Safe Starting Dose in Initial Clinical Trials for Therapeutics in Adult Healthy Subjects, a starting dose of [REDACTED] K0706 will be used for this first-in-human study.

In more detail, to estimate the potential human exposure at the [REDACTED] starting dose, [REDACTED] was performed on the [REDACTED] data (which used the [REDACTED] formulation) from the [REDACTED]. The [REDACTED] approach was based on the [REDACTED]
[REDACTED]
[REDACTED]
[REDACTED]
[REDACTED]
[REDACTED]
[REDACTED]
[REDACTED]

[REDACTED] These findings provide additional safety margin support for the starting dose. There is variability in the data between species, and the starting dose and schedule were selected conservatively to protect subject safety.

Subsequent to these PK studies using [REDACTED] was added to the clinical formulation to facilitate dissolution. [REDACTED] is generally recognized as a safe excipient. The estimated absolute bioavailability of the original [REDACTED] formulation ranged from [REDACTED]. Even a [REDACTED] improvement in predicted human exposure from this change will still be well below that of the NOAEL exposure by a considerable margin, further confirming the starting dose of [REDACTED] K0706 for this first-in-

human study. Finally, the NOAEL established in the [REDACTED] studies support the planned repeat dosing of CML subjects in Part B.

In agreement with its *in vitro* profile, K0706 shows potent activity in its *in vivo* models based on BCR-ABL and good systemic availability in oral administration in [REDACTED].

Additionally, to the proposed starting dose of [REDACTED] may be modified based on the data obtained from Part A of the study. The data from Part A of the study will help to confirm the expected bioavailability of the K0706 capsule formulation and examine the dose relationship in K0706 exposure in a homogenous study population. The systemic exposure of K0706 in Part A will allow prediction of multiple dose exposure possible in Part B. This information will help define the range of doses in Part B that would be predicted to achieve efficacious K0706 concentrations.

The initial administered dose will be the dose from Part A SAD study where acceptable safety was observed [e.g., 2 or more subjects do not develop Grade 2 or higher AEs (AEs; in the same biologic system that are not clearly and incontrovertibly related to something other than the IMP) in [REDACTED] subject cohort, or no subject develops AE Grade 3 or higher (that is not clearly and incontrovertibly related to something other than the IMP)]. Projections from PK parameters in the various PK species suggest that a once daily dosing schedule should not lead to significant drug accumulation; for this reason once daily dosing will be planned for subjects receiving multiple dose administrations.

Rationale for the study in Patients

The study will be an open-label dose-escalation study in subjects with BCR-ABL-related malignancies (see inclusion criteria for details). It will involve multiple doses per subject and will be used to determine the MTD and to help define the RP2D appropriate for these patient populations. Additionally, the conduct of the study in subjects will allow for drug activity assessments not possible with healthy volunteers. As is consistent with Phase 1 dose escalation multi-dose first in man studies, subjects will be selected to be resistant or intolerant to the local Standard of Care Therapy for their disease. Despite country differences, it is expected that such Standard of Care therapy will include at least 1 line of treatment with a CML TKI. Subjects enrolled should be resistant or intolerant to at least 3 TKIs or are not eligible (e.g., due to comorbidities, hypersensitivity to excipients, outside of the US - lack of insurance coverage) for their local country's regulatory authority approved and medically appropriate TKIs (e.g., a TKI that is effective against mutations in the patient's tumor).

6.1.1 Risk Assessment

BCR-ABL TKIs such as imatinib mesylate, dasatinib, nilotinib, bosutinib and ponatinib are used in the treatment of Ph+ leukemias and a number of AEs have been noted with their clinical use. While some of the observed AEs are common between the BCR-ABL TKIs used and contribute as a class effect, specific adverse reactions are associated with the structure of the BCR-ABL TKI used. Since K0706 is being developed as a TKI for the treatment of Ph+ leukemias, AEs commonly observed with the approved BCR-ABL TKI class of drugs may be observed with the clinical use of K0706 as well. Additionally, long term toxicity data in [REDACTED] and data from Part B of the study did [REDACTED] indicate any [REDACTED] [REDACTED]

The following AEs have been reported during clinical studies and clinical use of BCR-ABL TKIs such as imatinib [REDACTED] dasatinib [REDACTED] nilotinib [REDACTED] ponatinib [REDACTED] and bosutinib [REDACTED]. Similar AEs could be associated with the use of K0706, see Appendix II (Section 13.2) and the IB for more details:

- Fluid retention: It is advised to monitor subjects for development of signs and symptoms of fluid retention.
- Myelosuppression: It is advised to monitor complete blood counts regularly.
- Cardiac arrhythmias: Subjects should be advised to report signs and symptoms of slow or rapid heart rate. Drugs known to prolong the QT interval and strong CYP3A4 inhibitors should be avoided. Caution is recommended when administering to subjects with hepatic impairment.
- Heart failure: Subjects should be monitored for signs or symptoms consistent with cardiac dysfunction and should be treated appropriately.
- Hepatotoxicity It is advised to monitor liver function tests regularly.
- Pancreatitis: Caution is recommended in subjects with a history of pancreatitis
- Hemorrhage: Caution is indicated in subjects requiring medications that inhibit platelet function or anticoagulants.
- Pregnancy: Women should be advised of the potential hazard to the fetus and to avoid becoming pregnant.
- Tumor lysis syndrome: Correction of clinically significant dehydration and treatment of high uric acid levels are recommended.
- Compromised wound healing and gastrointestinal perforation.

Other drug specific AEs observed with the use of BCR-ABL TKIs include, hepatic impairment, neuropathy, ocular toxicity, and vascular occlusion (arterial and venous) with

the use of ponatinib and renal toxicity with bosutinib use. Sudden deaths and electrolyte disturbances have been reported with the use of nilotinib.

From the data available with clinical use of K0706, the most frequently observed treatment emergent adverse effects in the study were from the following System Organ Classes:

[REDACTED]
 [REDACTED]
 [REDACTED]
 [REDACTED]

Most drug related events were mild to moderate in intensity and resolved with or without treatment. These events are known with the use of TKIs and are expected for this class of drugs. For additional details, refer to IB.

6.1.2 Urgent safety measures

The Sponsor and Investigator should take appropriate urgent safety measures in order to protect the subjects of a clinical study against any immediate hazard to their health or safety. If such measures are taken the Sponsor shall (no later than 3 days from the date the measures are taken) give written notice to the licensing authority and the relevant Ethics Committee of the measures taken and the circumstances giving rise to those measures.

6.2 STUDY OBJECTIVES

6.2.1.1 Primary Objectives

The primary objectives of the study are to:

- To determine the MTD (or RP2D) of K0706 administered
- To evaluate the safety of K0706

6.2.1.2 Secondary objectives

The secondary objectives of the study are to:

- To evaluate the therapeutic activity of K0706
- To evaluate the PK of K0706 after multiple oral doses in subjects with the selected BCR-ABL-associated hematologic malignancies

6.2.1.3 Exploratory Objectives

The exploratory objectives of the study are to evaluate the genetic alterations that may correlate with K0706 resistance, such as:

- BCR-ABL mutation profile at therapy start (screening)
- BCR-ABL mutation profile at progression (should it occur)

6.3 INVESTIGATIONAL PLAN

6.3.1 Overall Study Design

The study will be an open-label, dose-ranging, single-agent, multicenter, multidose, dose escalation study initiated in subjects with Ph+CML (Ph+ CML include CML-CP, AP and BP [without the BCR-ABL T315I mutation]) and Ph+ ALL. Eligible subjects will be treated in [REDACTED] cycles of once-daily self-administered K0706. While K0706 should be preferably taken after [REDACTED], the subjects should be instructed to maintain [REDACTED] IMP dosing throughout the study.

To determine the MTD and/or the RP2D, the study will initiate with an accelerated titration dose-escalation design and transition to a 3+3 design when the first subject enrolled in the initial accelerated titration dose escalation cohort develops grade 2 or higher AE that is not clearly and incontrovertibly related to the underlying disease or concomitant medication.

The initial dose escalation cohorts can enroll at least 1 and up to 3 subject into each cohort. The subject enrolled into each cohort following the accelerated design of the initial escalation steps will receive the initial IMP administration, and continue to receive IMP at the same dose daily (unless [s]he qualifies for intra-subject escalation as described in Section 6.3.1.1. In cases where more than 1 subject have been entered in the accelerated titration component of the study, only the 1st subject will be evaluable unless the Sponsor and Investigator deem otherwise. If the first subject enrolled in this cohort does not experience a Grade 2 or higher AEs or DLTs during Cycle 1 of his/her study treatment

[REDACTED] the dose for the next subject(s) will be escalated to the next dose level. Enrollment into subsequent cohorts will proceed only after the current cohort has completed Cycle 1 of study treatment.

A subject administered a dose lower than the highest studied dose may have his/her dose increased up by one dose level at a time or to a dose that is 1 dose level below the highest studied dose, as per Investigator's discretion provided that the conditions stipulated in Section 6.3.1.1 are met.

In cases where more than one subject have been entered in the accelerated titration component of the study, only the 1st subject will be evaluable unless the Sponsor and Investigator deem otherwise. If this first subject enrolled in this cohort experiences a Grade 2 or higher AE that is not clearly and incontrovertibly related to the underlying disease or concomitant medications, then that cohort and all subsequent cohorts will follow the standard 3+3 design. All toxicities will be considered when making decisions regarding drug escalation increments or discontinuations, unless they are clearly and incontrovertibly related to the underlying disease or concomitant medications. When more than 1 subject is enrolled, enrollment may occur concurrently and the subjects may be administered their IMP concurrently.

For the cohorts where the 3+3 design applies, 3 subjects will be enrolled initially. If 2 of these subjects experience a Grade 2 or more toxicity (that is not clearly and incontrovertibly related to the underlying disease or concomitant medications), subsequent cohorts will be escalated according to smaller increments. Further, if there are no DLTs in the first 3 subjects, dose-escalation to the next higher dose level may proceed. If 1 of the 3 subjects experiences a DLT, that dose level will be expanded to 6 subjects (3 additional subjects will be enrolled). If 2 subjects at a given dose level experience a DLT, the MTD will have been exceeded. The next lower dose level will be expanded to 6 subjects, or if 6 subjects have already been enrolled and no more than 1 of the 6 subjects experienced a DLT, then this lower dose level will be considered the MTD.

Once the MTD or RP2D is established, the Sponsor and Principal Investigators may elect to add up to 12 additional subjects in each of the subgroups as expansion cohorts (i.e.: CML-CP, CML-AP, CML-BP, T315I CML-CP and Ph+ ALL) using the modified toxicity probability interval design starting at the MTD or RP2D for each subset of subjects. The T315I CML-CP cohort will be opened only when sufficient plasma levels found to be active preclinically in the T315I clone are achieved in the dose escalation cohorts. Until then Subjects with T315I mutations will not be enrolled in any part of the study.

Subject(s) in the subgroup expansion cohorts will start at MTD or RP2D achieved in the dose escalation cohorts. Initially, three subjects will be enrolled into each of the subgroup expansion cohort and monitored for DLTs. An internal Data Monitoring Committee (iDMC) will be convened after the 3 subjects have completed the DLT observation period. Stopping rules and subsequent dosing strategy will be made as per the algorithm described in the schematic for modified toxicity probability interval as depicted in Figure 6-2. The iDMC may recommend enrolling subsequent subjects at the same dose level if escalation criteria are met (e.g. DLTs in $\leq 1/3$ subjects) depending on emerging safety-efficacy profile. The second set of up to 9 subjects will be enrolled if stopping rule is not met after review of data from first 3 subjects. Separate MTD or RP2D may be identified for CML-CP, CML-AP, CML-BP, T315I CML-CP and Ph+ ALL.

The RP2D will be that dose level selected for further clinical evaluation; selection of the RP2D will be based on safety, tolerability, preliminary anticancer activity findings, and the observed trough blood level for K0706 relative to levels found to be active preclinically.

The decision to advance to the next dose level will only occur after careful evaluation of safety and tolerability data for a given dose level by the Sponsor and Principal Investigator after completion of Cycle 1; data from later cycles of treated subjects may be taken into consideration in this decision.

Additionally, an internal data monitoring committee consisting of members from the Sponsor, the investigative site, the CRO and an independent member will be formed to oversee the study. A formal charter will be generated that will describe the responsibilities of this group and submitted as an IND amendment prior to the initiation of Part B.

Details of the dose escalation process and doses to be administered are provided in Section 6.3.1.1.

A subject experiencing a DLT may continue therapy with a reduced dose of K0706. Subjects who experience a DLT and recover, may be treated (at the Investigator's discretion) at the next lower dose level until disease progression or other events requiring further dose reduction exist. For cohorts at Dose Level 2 or higher, a further dose reduction (i.e., up to 2 levels lower than their originally assigned dose) may be implemented in the case of a further DLT or other non-DLT events requiring a dose reduction, if and when the event leading to dose reduction returns to Grade 1 or lower in severity. Further dose reduction or delay or both may be implemented basis joint discussion between investigator and sponsor's medical monitor basis evaluation of subject's clinical condition. The reduced dose may be re-escalated to the original or higher dose (ie: dose for which safety has been established in the dose escalation cohort) at Investigator's discretion considering subject safety and response to the study drug and in consultation with Sponsor's medical monitor. Subjects experiencing a Grade 4 toxicity attributable to K0706 will undergo dose reduction and dose delays as per guidance provided in Section 6.4.2.1. [REDACTED]

The study will consist of a screening wherein all the required clinical and laboratory investigations to establish the eligibility of the patient for the trial is completed. Subject's disease diagnosis and status will be confirmed using the pathology reports available with the subject at the time of screening initiation. Only the latest pathology reports, subsequent to which there has been no change in therapy (with a potential to affect the disease course), will be considered for screening. [REDACTED]

Re-screening: [REDACTED]. Re-screening requests will be reviewed on case-by-case basis in consultation with the medical monitor of the CRO and/or Sponsor. Reasons that may qualify for a re-screening include 1) expiry of screening period due to personal issue or timing or prior withdrawal of consent by subject 2) stabilization or discontinuation of prohibited concomitant medication 3) medical condition that has now resolved. However, re-screening is not allowed if the previous

failure was because of eligibility criteria that are unlikely to change (example: h/o allergy to the excipients, significant drug abuse, involvement in planning of study, confirmed incorrect disease diagnosis or re-screening puts the subject's safety at risk). In case of re-screening, the subject will be assigned a different screening number.

Subjects will enter the study center [REDACTED] on Day 1 to receive the first administration of IMP and will complete the required assessments and sample collections ([REDACTED]). While K0706 should be preferably taken after [REDACTED], the subjects should maintain [REDACTED] IMP dosing in all the cycles. Subjects may be admitted a day prior to Cycle 1 Day 1 dosing and if required stay overnight at the study center on Cycle 1 Day 1, based on Investigator's discretion. Subjects will complete the assessments on Cycle 1 Day 2 and may remain in the study center overnight for observation, at the discretion of the Investigator. Subjects will return for follow-up assessments [REDACTED] in Cycle 1 on Days [REDACTED].

Cycle 2 will have similar [REDACTED] sample collections on Day 1, and subjects will be required to return to the study center on Days [REDACTED] for [REDACTED] samples and other follow-up assessments. From Cycle 3 onwards, subjects will only be required to return to the study center once every 3 [REDACTED].

Note: The last observation/evaluations for each cycle may coincide with the Day 1 of next cycle e.g., Cycle 6 Day [REDACTED] observation may coincide with Cycle 7 Day 1). [REDACTED] samples will be collected on the day of the study visit from Cycle 3 onwards.

Subjects will remain on study treatment for approximately 60 months (i.e.: 5 years from 1st K0706 dosing), or until intolerance, subject withdraws from the study, or progression of disease. Subjects who discontinue the study will be followed up for survival (survival assessment includes information about subject survival and other anticancer therapies) every 3 months after the IMP discontinuation till 60 months from their first dose of K0706 or until death, withdrawal of consent, or the end of the study, whichever comes first.

[figure not shown]
Treatment beyond 60 months will be considered, provided the Investigator considers that the subject is benefiting from K0706 therapy. Subjects who continue to receive K0706 beyond 60 months will be followed up for safety, survival and response assessments. Information about subject's survival and disease response will be collected at the follow up visits every 3 months in these subjects.

Medical Care of Subjects after the End of Treatment Visit:

After a subject has completed the study or has withdrawn early from the study, usual treatment (as per the local standards of care) may be administered, if required, in accordance with the study center's generally accepted medical practice and depending on the subject's individual medical needs. The Sponsor will not have any role to play in further treatment and the treatment regimen followed will be outside the purview of the study protocol. Information about subject's survival and anticancer therapies will be

collected every 3 months for approximately 60 months from the subject's first dose, by telephone contact, medical record review, and/or study center visits until death, withdrawal of consent, or the end of the study, whichever comes first. This information will be documented by the study center personnel in the subject's source documents and the electronic data capture system

Schematic of the design is presented in Figure 6-1 Schematic for the Study: PART B

- A. If medically warranted, subjects may be admitted to the study center overnight on Cycle 1 Day 1.
- B. The last observation and assessments for each cycle will coincide with the Day 1 of next cycle. The window period for Day 1 of every cycle in ± 3 days

[REDACTED]

[REDACTED]

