6.3.1.1 Dose Escalation criteria

The decision to advance from one dose level to the next dose level will only occur after careful evaluation of all the available safety and tolerability data for a given dose level by the Sponsor and Principal Investigators after completion of Cycle 1; data from later cycles of treated subjects may be taken into consideration in this decision.

Progression to the next higher dose will only occur if the previous dose level was deemed to be safe and well tolerated by the Principal Investigator and the Sponsor.

An appropriate interval ([REDACTED]) will separate the investigation of dose levels to permit a timely review and evaluation of safety data prior to proceeding to the next higher dose level.

When it is not appropriate to escalate the dose then the same dose, a previous dose or an intermediate dose may be given following discussion between the Principal Investigators and Sponsor. Additional dose levels may also be investigated depending upon the results of the safety data from the previous dose levels and consideration of the preclinical toxicology data.

All data reviewed at the dose escalation meeting between the Principal Investigators and Sponsor ([REDACTED]) will be subjected to a quality review.

In cases where more than one subject have been entered in the accelerated titration component of the study, only the 1st subject will be evaluable unless the Sponsor and Investigator deem otherwise. If the first subject enrolled in this cohort does not experience Grade 2 or higher AEs or DLTs during Cycle 1 of his/her study treatment (i.e., [REDACTED])

[figure not shown]
[REDACTED] the dose for the next subject(s) will be escalated to the next dose level. Enrollment into subsequent cohorts will proceed only after the current cohort has completed Cycle 1.

A subject administered a dose lower than the highest studied dose may have his/her dose increased up by one dose level at a time or to a dose that is 1 dose level below the highest studied dose, as per Investigator's discretion provided that:

1. The dose cohort to which the patient is being escalated has been completed (e.g., 1 cycle has been completed for all subjects).
2. The subject has not previously experienced a DLT.
3. The patient has no residual drug-related toxicity that is greater than grade 1.

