Any results from intra-subject dose escalations will not affect inter-subject dose escalations unless the Investigator and Sponsor agree that intra-subject escalation information reasonably alters the potential benefit-risk ratio for subsequently treated subjects.

Dose escalations should occur at the beginning of a new cycle. Safety findings from intra-subject escalations will not be used for determination of the MTD of a regimen.

Abbreviations: D: Day, DLT: Dose limiting toxicity, MTD: Maximum tolerated dose.

In cases where more than 1 subject have been entered in the accelerated titration component of the study, only the 1st subject will be evaluable unless the Sponsor and Investigator deem otherwise. If this first subject enrolled experiences a Grade 2 or higher AE that is not clearly and incontrovertibly related to the underlying disease or concomitant medications, then that cohort and all subsequent cohorts will follow the standard 3+3 design. All toxicities will be considered when making decisions regarding drug escalation increments or discontinuations, unless they are clearly and incontrovertibly related to the underlying disease. When more than 1 subject is enrolled, enrollment may occur concurrently.

For the cohorts where the 3+3 design applies, 3 subjects will be enrolled initially. If there are no DLTs in the first 3 subjects, dose-escalation to the next higher dose level may proceed. If 1 of the 3 subjects experiences a DLT, that dose level will be expanded to 6 subjects (3 additional subjects will be enrolled). If 2 or more of 6 subjects at a given dose level experiences a DLT, the MTD will have been exceeded.

A DLT is defined as the occurrence of any of the following unless clearly and incontrovertibly related to the underlying disease. The hematological DLTs have been defined as per the Phase of CML:

- [REDACTED]
[REDACTED]
[REDACTED]
- Missed $\geq 25\%$ of doses over 28 days due to toxicity in Cycle 1
- Any grade of toxicity requiring dose reduction or discontinuation of IMP within the 28 day DLT assessment period [REDACTED]

Hematological DLT, as per the Phase of the Chronic Myeloid Leukemia:

- Hematological DLTs for subjects in CML-Chronic Phase
 [REDACTED] for ≥ 28 days off the study drug treatment or [REDACTED]
 [REDACTED] ≥ 7 days off the study drug (i.e.: after treatment interruption)
- Hematological DLTs for Subjects in CML-Accelerated Phase
 [REDACTED] for ≥ 28 days off the study drug treatment or [REDACTED]

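### In Part B, two dosing rules give opposite answers on whether a subject reduced after a DLT may later go above the original dose

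*Protocol*

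**What the plan says.** **Rule for dose increases.** Protocol 6.3.1.1 states: "A subject administered a dose lower than the highest studied dose may have his/her dose increased up by one dose level at a time". The alternative it offers is a move to the level just under the highest studied. Either step requires three conditions. The target cohort must be complete, residual drug-related toxicity must not exceed grade 1, and, as condition 2, "The subject has not previously experienced a DLT". The Part B methodology in the Protocol Summary carries the same list. Section 6.3.1 brings it in by reference: "as per Investigator's discretion provided that the conditions stipulated in Section 6.3.1.1 are met". SAP 3.1 repeats it under Dose Escalation Schema.

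**Rule for reduced doses.** A separate paragraph, in both 6.3.1 and 6.3.1.1, opens: "A subject experiencing a DLT may continue therapy with a reduced dose of K0706". A subject who recovers may be treated "at the next lower dose level until disease progression or other events requiring further dose reduction exist". The paragraph then covers further reduction after another DLT or a non-DLT event, and goes on: "The reduced dose may be re-escalated to the original or higher dose". A parenthesis restricts the target to a "dose for which safety has been established in the dose escalation cohort". The decision is the Investigator's, weighing the subject's safety and response, in consultation with the Sponsor's medical monitor. SAP 3.1 repeats the re-escalation sentence with the same limits.

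**The concern.** Section 6.3.1.1 contains both rules. One makes freedom from any earlier DLT a precondition for raising a subject's dose. The other, in a paragraph that starts from subjects who have had a DLT, allows the dose to be raised again and sets the ceiling above where the subject began.

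The first thing at stake is the individual subject. The rules disagree on whether someone with a documented DLT may later receive more drug than the dose at which it occurred, and two sites could act differently, each with support in the protocol.

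The second is the analysis. Section 6.3.1.1 and SAP 3.1 keep safety findings from intra-subject escalations out of the MTD determination. If post-DLT re-escalation is not clearly inside or outside that category, the handling of its safety findings is not fixed in advance.

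**Working it through.** No arithmetic applies, so the check sets the two rules side by side and applies them to one subject.

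**Step 1: do both rules reach the same subject?** The increase rule applies to anyone on a dose below the highest studied dose, and it does not exempt subjects who are there because of a reduction. The re-escalation paragraph begins with DLT subjects on a reduced dose. The DLT definition in 6.3.1.1 includes "Any grade of toxicity requiring dose reduction or discontinuation of IMP within the 28 day DLT assessment period", unless clearly due to the underlying disease, so a toxicity-driven reduction in that window itself makes the subject a DLT subject. Such a subject falls under both rules.

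**Step 2: do the rules give different answers?** Label the dose levels L1 < L2 < L3 < L4. A subject is assigned L2, has a DLT there, is reduced to L1 and recovers. L2 finishes with 1 DLT in 6 subjects, and L3 clears with 0 in 3. Assume that established safety means what the Protocol Summary calls tolerated (fewer than 2 DLTs in 6, or fewer than 1 in 3); the re-escalation sentence does not define it. On that assumption L2 and L3 both qualify, and L4 is the highest dose studied.

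| Proposed step | Increase rule | Re-escalation sentence |
|---|---|---|
| Stay at L1 | Not engaged | Not engaged |
| L1 to L2 (original dose) | Condition 2 not met | Permitted, within its limits |
| L1 to L3 (above the original) | Condition 2 not met | Permitted, within its limits |

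The rules agree while the subject stays at L1 and part company only when an upward step is proposed.

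**Step 3: can the visible text reconcile them?**
- *L1 to L2.* Re-escalation could be read as restoring an assigned dose, a different act from an elective increase. The documents do not say this, but the words allow it.
- *L1 to L3.* This takes the subject beyond the assigned level, so it cannot be described as restoring anything.
- *The limits on re-escalation.* Established safety is judged on a cohort, while condition 2 looks at the individual's own history. Discretion and consultation govern who decides. None of them sets condition 2 aside.
- *The sentence on treatment at the next lower level.* It contains no return upward, so it does not support re-escalation.

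**Step 4: what follows for the analysis?** The MTD exclusion covers intra-subject escalations, and neither document says whether re-escalation after a DLT is one. SAP 15.1 counts subjects with dose escalations, and SAP 15 presents safety by dose, again without addressing the point.

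**The case against.** The strongest reply is that the rules have different subjects: condition 2 governs elective escalation, and the re-escalation sentence belongs to dose modification. That paragraph also mentions reductions for non-DLT events. Treatment lasts about 60 months, so many reductions could fall after the 28-day window and involve no DLT. For those subjects condition 2 is satisfied and nothing conflicts. This stands for non-DLT reductions and offers a possible reading for a return to the original dose. It does not explain going higher after a DLT.

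Second, the permission is guarded by established safety, subject-level judgement and the medical monitor. A reader might infer that a subject with a DLT may be given more drug on the Investigator's word alone. The text does not support that.

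Third, text next to the re-escalation sentence is redacted in 6.3.1, 6.3.1.1 and SAP 3.1, as is most of Protocol 6.4.2.1 on dose delays and reductions. A reconciling condition could lie there, so the finding can speak only for the visible wording.

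Fourth, the analytic consequence is modest. Part B has no formal testing, its efficacy endpoint is secondary, and Section 7.1 says the RP2D has been established. SAP 15.1 already tabulates reductions and escalations, though it does not single out re-escalation after a DLT. This stands, and it leaves the safety rule as the main reason to act.

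**Conclusion.** The inconsistency holds in a limited form. For a Part B subject reduced after a DLT, the visible text both bars and allows a later dose above the original. For a return to the original dose the text is ambiguous.

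Three stronger readings are not supported:
- A reader might infer that every DLT subject who continues on drug is affected. Both rules allow continuing on a reduced dose. They diverge only if an upward step is later proposed, and a step above the original also needs a higher dose with established safety.
- A reader might infer an effect on discontinuation. Neither rule requires stopping, and no such effect is shown.
- A reader might take the subject described in Section 5.2 as restarted after a DLT as a case of re-escalation. The restart dose is redacted, and the visible text identifies no subject re-escalated after a DLT.

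The number of subjects concerned is therefore unknown and could be zero. The conclusion assumes that the redacted text holds no exception and that the original dose is the one at which the DLT occurred. It takes no view on which rule is right. Because the rule bears on subject safety and is cheap to clarify, it should be reconciled.

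**What to change.** 1. Reconcile the Part B methodology in the Protocol Summary, Protocol 6.3.1 and 6.3.1.1, and SAP 3.1, so that one rule, chosen by the clinical team, governs dose increases after a DLT. It should address the original dose and any higher dose separately, and say how it relates to condition 2.
2. State in Protocol 6.3.1.1 and SAP 3.1 whether re-escalation after a DLT counts as intra-subject escalation for the exclusion from MTD determination.
3. From dosing data already collected, list any Part B subject re-escalated above the dose at which a DLT occurred.

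The cost is a small edit in several places across both documents, plus one listing. No new data are needed.
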